#### **11.4.3 Procedures for Reporting Drug Exposure During Pregnancy and Birth Events**

If a woman becomes pregnant or suspects that she is pregnant while participating in this study, she must inform the investigator immediately and permanently discontinue study drug. The sponsor-investigator must fax a completed Pregnancy Form to the Takeda Pharmacovigilance or designee immediately (see Section 11.4.2). The pregnancy must be followed for the final pregnancy outcome (i.e., delivery, still birth, miscarriage) and Takeda Pharmacovigilance or designee will request this information from the sponsor-investigator.

If a female partner of a male patient becomes pregnant during the male patient's participation in this study, the sponsor-investigator must also immediately fax a completed Pregnancy Form to the Takeda Pharmacovigilance or designee (see Section 11.4.2). Every effort should be made to follow the pregnancy for the final pregnancy outcome.

#### **11.4.4 Requirements for Reporting Product Complaints to Millennium**

A product complaint is a verbal, written, or electronic expression that implies dissatisfaction regarding the identity, strength, purity, quality, or stability of a drug product. Individuals who identify a potential product complaint situation should immediately contact Millennium Pharmaceuticals (see below) and report the event. Whenever possible, the associated product

should be maintained in accordance with the label instructions pending further guidance from a Millennium Pharmaceuticals Quality representative.

A medication error is a preventable event that involves an identifiable subject and that leads to inappropriate medication use, which may result in subject harm. While overdoses and underdoses constitute medication errors, doses missed inadvertently by a subject do not. Individuals who identify a potential medication error situation should immediately contact Millennium Pharmaceuticals (see below) and report the event.

For Product Complaints or Medication Errors, call
 
For ADCETRIS or PIPELINE Products:
 
Phone: [REDACTED]
 
Email: [REDACTED]

--------------------------------------------------------------------------------------------------------------------------------------------------------------------------------------------------------------------------------------------------------------------------------------------------

Product complaints in and of themselves are not AEs. If a product complaint results in an SAE, a MedWatch 3500a should be completed and sent to Millennium Pharmaceuticals Pharmacovigilance

### 11.5 Expedited Reporting to the Food and Drug Administration (FDA)

The Overall PI, as study sponsor, will be responsible for all communications with the FDA. The Overall PI will report to the FDA, regardless of the site of occurrence, any serious adverse event that meets the FDA's criteria for expedited reporting following the reporting requirements and timelines set by the FDA.

### 11.6 Expedited Reporting to Hospital Risk Management

Participating investigators will report to their local Risk Management office any participant safety reports or sentinel events that require reporting according to institutional policy.

### 11.7 Routine Adverse Event Reporting

All Adverse Events **must** be reported in routine study data submissions to the Overall PI on the toxicity case report forms. **AEs reported through expedited processes (e.g., reported to the IRB, FDA, etc.) must also be reported in routine study data submissions.**

Abnormal laboratory values or diagnostic test results constitute AEs only if they induce clinical signs or symptoms or require treatment or further diagnostic tests

Hospitalization for elective surgery or routine clinical procedures that are not the result of an AE (e.g., surgical insertion of central line) should not be recorded as an AE.

Disease progression should not be recorded as an AE, unless it is attributable to the study regimen by the site investigator.

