#### Prevention/Prophylaxis

- Follow fasting serum glucose levels during clinic visits.
- Monitor home glucometer test results.
- Check HbA1c levels every 3 months during therapy.

- 
- Life-style modifications, as appropriate (balanced diet, limit alcohol consumption, increase physical activity).
  - Most episodes of Grade 1 and 2 hyperglycemia respond quickly to oral metformin.
  - Early initiation of therapy is recommended to prevent higher grade hyperglycemia.
  - Fasting blood glucose levels  $\geq 150$  mg/dL by glucometer should be followed by closer monitoring of serum glucose and possible intervention.
- 

Abbreviations: dL = deciliters; mg = milligrams; ULN = upper limit of normal.

On the basis of the clinical experience in TAK-228 trials, most episodes of hyperglycemia observed occurred within the first 60 days after initiation of treatment with TAK-228 and have been either Grade 1 or Grade 2, and have responded quickly to oral metformin. Hyperglycemia has not been dose-limiting since the institution of a standard regimen for early treatment of hyperglycemia.

All subjects developing hyperglycemia during the study should have their glucose closely monitored by study staff. The site investigator may choose to continue close monitoring of subjects who develop Grade 1 hyperglycemia (fasting glucose  $>ULN \leq 160$  mg/dL) or, alternatively, consider initiating treatment with an oral hypoglycemic agent, such as metformin. All subjects with  $\geq$ Grade 2 hyperglycemia (fasting glucose  $>160$  mg/dL) must be treated aggressively with oral hypoglycemic agents and/or insulin as clinically indicated. The site investigator should consult an endocrinologist, if needed, to aid in optimizing the subject's hyperglycemia treatment plan.

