### 11.1 Expected Toxicities

#### 11.1.1 Adverse Event List

##### 11.1.1.1 Adverse Event List for TAK-228

Among the 335 subjects who had received  $\geq 1$  dose of study drug as of the clinical data cutoff date (09 December 2014), 18 deaths had occurred within 30 days of the last dose, including 7 in Study INK128-001, 2 in Study INK128-002, and 9 in Study INK128-003. One death (ventricular fibrillation and cardiac arrest; Study INK128-001) was considered related to TAK-228. At least 1 treatment-emergent SAE, regardless of causality, had been reported in 125/335 subjects (37%). Across the studies and regardless of causality or dosing regimen, the most common treatment emergent adverse events (TEAEs) included nausea, fatigue, hyperglycemia, vomiting, diarrhea, stomatitis, and decreased appetite.

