### 11.4.2 Requirements for Reporting SAEs to Millennium

Adverse Events may be spontaneously identified by the patient and/or in response to an open question from study personnel or revealed by observation, physical examination, or other

diagnostic procedures. Any clinically relevant deterioration in laboratory assessments or other clinical finding is considered an AE. When possible, signs and symptoms indicating a common underlying pathology should be noted as one comprehensive event.

Adverse Events which are **serious** must be reported to Takeda Pharmacovigilance (or designee) from the time of consent up to and including 30 days after administration of the last dose of TAK-228. Any SAE that occurs at any time after completion of TAK-228 treatment or after the designated follow-up period that the sponsor-investigator and/or sub-investigator considers to be related to any study drug must be reported to Takeda Pharmacovigilance (or designee). In addition, new primary malignancies that occur during the follow-up periods must be reported, regardless of causality to study regimen, for a minimum of two years after the last dose of the investigational product, starting from the first dose of study drug. All new cases of primary malignancy must be reported to Takeda Pharmacovigilance (or designee).

Planned hospital admissions or surgical procedures for an illness or disease that existed before the patient was enrolled in the trial are not to be considered AEs unless the condition deteriorated in an unexpected manner during the trial (e.g., surgery was performed earlier or later than planned). All SAEs should be monitored until they are resolved or are clearly determined to be due to a patient's stable or chronic condition or intercurrent illness (es).

Since this is an investigator-initiated study, the principal investigator [name] also referred to as the sponsor-investigator, is responsible for reporting serious adverse events (SAEs) to any regulatory agency and to the sponsor-investigator's EC or IRB.

Regardless of expectedness or causality, all SAEs must also be reported in English to Takeda Pharmacovigilance or designee:

**Fatal and Life Threatening SAEs** within 24 hours of the sponsor-investigator's observation or awareness of the event

**All other serious (non-fatal/non life threatening) events** within 4 calendar days of the sponsor-investigator's observation or awareness of the event

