#### **12.2.2 Definition of Secondary Endpoints**

- Safety and tolerability according to NCI CTCAE version 4.0
- Progression-free survival (PFS): time from registration to the earlier of (radiographic) progression based on RECIST 1.1 or death due to any cause. Subjects alive without disease progression are censored at date of last disease evaluation.
- Overall survival (OS): time from registration to death due to any cause, or censored at date last known alive.

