### **12.3 Sample Size and Accrual**

Forty subjects with metastatic RCC will be enrolled for a goal of 38 evaluable subjects (assuming 5% not evaluable). The two-stage single arm phase II study is designed to detect an improvement in response rate from 5% to 20%. Assuming a type I error of 0.05 and targeting 90% statistical power, 20 patients will be accrued (for 19 evaluable) in the first stage. The first interim analysis will occur when the first 8 week imaging assessment for response data is available for all 20

patients. If 1 or more responses are observed, the accrual will continue to the second stage. Twenty (for 19 evaluable) additional patients will be accrued in the second stage. TAK-228 will be declared ineffective in this study if <5 responses are observed. It will be considered worthy of further study if more than 4 ( $\geq 5$ ) responses are observed.

The design operating characteristics are as follows:

Hypothesis	#s responses at stage I	Prob(stop at first stage)	Overall # responses	Prob(Rx declared inactive)	Design Statistics
Ho: ORR=0.05	<1	38%	$\leq 4$	96%	True type I error 0.04
Ha: ORR=0.2	<1	1.4%	$\leq 4$	10%	Power: 90%

The 90% confidence intervals for the response rate in a two-stage phase II design are summarized as below. The calculation employed the method of Atkinson and Brown (1985) *Biometrics* 741-744

Observed # of responses	Response rate	90% CI
4/38	0.105	(0.04, 0.23)
5/38	0.13	(0.05, 0.26)
6/38	0.16	(0.07, 0.29)
7/38	0.18	(0.09, 0.32)

The accrual is expected to be 3 subjects every month for 14 months to complete enrollment with additional follow-up to 2 years for disease progression or survival. The study is expected to last approximately 40 months.

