#### 12.4 Analysis Datasets

Population	Definition
Enrolled	This will comprise all subjects who meet the eligibility criteria and are registered onto the study.
Evaluable	Subjects who receive at least one dose of trial drug TAK-228 and have at least one response assessment or die before any evaluation.
Safety	All subjects receiving at least one dose of TAK-228 will be included in analysis unless otherwise specified.

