#### **12.4.2 Analysis Plans for Secondary Objectives**

**Safety and Tolerability:** All adverse events recorded during the trial will be summarized for the safety population. The incidence of events that are new or worsening from the time of first dose of treatment will be summarized according to system organ class and/or preferred term, severity (based on CTCAE version 4.0 grade), type of adverse event, and relation to study treatment. Deaths reportable as SAEs and non-fatal serious adverse events will be listed by subject and tabulated by primary system organ class, and type of adverse event.

**PFS and OS:** PFS and OS will each be summarized using the product-limit method of Kaplan-Meier. Median times for each endpoint will be presented with two-sided 90% confidence intervals estimated using log(-log(survival)) methodology. Kaplan-Meier estimates of PFS at 6 or 12 months after treatment initiation may also be presented with two-sided 90% confidence intervals.

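### Two sections define laboratory adverse events differently and only recorded events are summarised, so low-grade laboratory changes may be missed or recorded inconsistently

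*Combined protocol and SAP*

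**What the plan says.** Two sections of the protocol state when a laboratory change is an adverse event (AE).

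- Section 11.4.2, on SAE reporting to the drug supplier: "Any clinically relevant deterioration in laboratory assessments or other clinical finding is considered an AE". It does not define clinical relevance.
- Section 11.7, on routine reporting, sends all AEs to the toxicity case report forms and then states: "Abnormal laboratory values or diagnostic test results constitute AEs only if they induce clinical signs or symptoms or require treatment or further diagnostic tests".

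Neither section refers to the other or takes precedence.

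Safety is a secondary endpoint, given in Section 12.2.2 as "Safety and tolerability according to NCI CTCAE version 4.0". The analysis in Section 12.4.2 reads: "All adverse events recorded during the trial will be summarized for the safety population". It reports events that are new or worse since first dose, by grade, but plans no laboratory grade or shift table. The safety population in Section 12.4 is defined thus: "All subjects receiving at least one dose of TAK-228 will be included in analysis unless otherwise specified".

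Laboratory-detected toxicity is expected with this drug. Section 11.1.1.1 says of earlier studies that "the most common treatment emergent adverse events (TEAEs) included nausea, fatigue, hyperglycemia" among others. At the lowest grade, Section 6.3.1 leaves the response open: "The site investigator may choose to continue close monitoring of subjects who develop Grade 1 hyperglycemia", or may consider an oral agent instead.

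**The concern.** The safety summary can contain only what sites record as AEs, and the protocol gives sites two tests for recording a laboratory change. Section 11.4.2 turns on clinical relevance. Section 11.7 turns on symptoms, treatment or further tests. Section 11.7 taken alone also depends partly on practice, because the same mild glucose rise can qualify where the investigator treats it and may not where the investigator watches it.

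At stake is the description of low-grade metabolic and hepatic toxicity in a single-arm study. Any-grade rates of hyperglycaemia, hyperlipidaemia and transaminase elevation could reflect recording habits as well as the drug, and a reader could not separate the two. The grades themselves are mostly numeric cut-offs on values the study calendar already collects.

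**Working it through.** The plan states no laboratory AE rate, so there is no figure to reproduce. The check is textual.

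**1. How the two rules treat an asymptomatic change.** The planned responses come from Tables 5, 7 and 14 (Sections 6.3.1, 6.3.3 and 6.3.8).

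| Analyte | Planned response at Grade 1 | Planned response at Grade 2 or above | Section 11.7 test at Grade 1 | Section 11.4.2 test at Grade 1 |
|---|---|---|---|---|
| Fasting glucose | Close monitoring; treatment optional | Glucose-lowering treatment | Depends on whether it is treated and whether monitoring counts as further testing | Depends on the reading of relevance |
| Lipids | None | Treatment by standard guidelines | Not met | Depends on the reading of relevance |
| AST/ALT | None | At least weekly liver tests; search for other causes | Not met | Depends on the reading of relevance |
| Blood counts, creatinine | No table of their own (creatinine at most under the general Table 13, which has no numeric cut-offs) | As at Grade 1 | Depends on local action | Depends on the reading of relevance |

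For glucose, lipids and AST/ALT, the planned response from Grade 2 upwards is treatment or extra testing. That satisfies Section 11.7 and would ordinarily count as clinically relevant, so the rules converge. The uncertainty is at Grade 1, and for analytes with no table of their own.

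**2. Scale.** Section 12.3 plans 40 subjects. If all are treated, one reclassified subject moves a rate by 1/40 = 2.5 percentage points.

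Going further needs assumptions that the documents do not supply. Let T be the true any-grade rate, g the share of cases that are Grade 1, asymptomatic and untreated, and w the share of subjects at sites applying Section 11.7. Suppose also that Section 11.4.2 captures every Grade 1 change. Then:

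reported rate = T × (1 − g × w)

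With T = 50% (20/40):

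| g | w = 0 | w = 0.5 | w = 1 |
|---|---|---|---|
| 20% | 50% | 45% | 40% (16/40) |
| 40% | 50% | 40% | 30% (12/40) |
| 60% | 50% | 35% | 20% (8/40) |

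The gap between the rules is T × g. Over T = 30% to 70% and g = 20% to 60% it runs from 0.30 × 0.20 = 6 points to 0.70 × 0.60 = 42 points. For comparison, the exact 90% interval for 20/40 is 36.1% to 63.9%, a half-width of (63.9 − 36.1)/2 = 13.9 points. A range this wide, resting on assumed inputs, shows that the size is unknown; it is not an estimate.

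**3. Can grades be derived from laboratory values?** The Section 7 calendar schedules blood counts and the metabolic panel (including glucose, AST, ALT and creatinine) at screening and every listed clinic visit. Fasting lipids are scheduled at screening, Day 1 of each cycle, every 8 weeks and discontinuation, but not at Cycle 1 Days 8, 15 and 22 or at Day 15 of Cycles 2 and 3.

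Two limits apply. Section 14.2 allows standard-of-care results to be entered selectively in the database. The calendar footnotes also differ on fasting: footnote 3 asks for it before the metabolic panel on Day 1 only, footnote 6 for serum glucose at each clinic visit.

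**4. Why shift from baseline.** Section 3.1 admits triglycerides up to 300 mg/dL, and Table 7 grades values above 150 and up to 300 as Grade 1. It admits AST/ALT up to 2.5×ULN, or 5×ULN with liver metastases, values that reach Grades 1 and 2 in Table 14. A worst-grade table without baseline would mix prior abnormality with change on treatment.

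**The case against.** The strongest reply is that the sections have different jobs. Section 11.4.2 concerns SAE reporting to the supplier; Section 11.7 governs the case report forms that feed the summary and can be read as spelling out what clinical relevance means. On that reading there is one rule, and limiting laboratory AEs to those with symptoms or action is a coherent choice. This has force, but the sentence in Section 11.4.2 is worded as a general definition and nothing says Section 11.7 interprets it.

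Four stronger inferences should be resisted.

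- A reader might infer that Grade 1 lipid and AST/ALT changes are AEs under Section 11.4.2 or under CTCAE but not under Section 11.7. The documents do not support this. A change needing no action may not be clinically relevant, so both rules may exclude it. CTCAE is used here to grade events (Section 11.2), not to decide what an event is.
- A reader might infer that hyperglycaemia will be under-counted. Table 5 asks for close monitoring even at Grade 1, and Section 6.3.1 has subjects report home values of 150 mg/dL or more and has home-detected hyperglycaemia confirmed in clinic. Much of it will plausibly meet the further-test condition.
- A reader might infer that sites will in fact apply different rules. The text permits that but does not show it; Appendix E provides for training and for monitoring of adverse events.
- A reader might quote 6 to 42 points as the effect. That range assumes the disputed reading of Section 11.4.2.

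**Conclusion.** The point holds as a minor improvement. The two sections are worded differently, neither is said to prevail, and the safety analysis uses recorded AEs only. Asymptomatic laboratory changes that prompt no treatment or further test may therefore be omitted or recorded inconsistently.

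The effect is confined mainly to Grade 1 and any-grade rates of glucose, lipid and AST/ALT changes, and to analytes without their own management table. Rates at Grade 2 or above for the three named groups should change little, on the assumption that sites follow Tables 5, 7 and 14. No size can be drawn from the documents beyond 2.5 points per reclassified subject among 40. The primary endpoint and the two-stage decision rule do not use AE recording and are unaffected.

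**What to change.** 1. Reconcile Sections 11.4.2 and 11.7 into one laboratory AE definition and use it in both. If clinical relevance is kept as the test, define it.
2. In Section 12.4.2, add a table of worst post-baseline CTCAE v4.0 laboratory grade, with shift from baseline, in the safety population. Cover the scheduled analytes: glucose, lipids, AST/ALT, creatinine and blood counts. Grades derived this way do not depend on which recording rule a site applied.

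The cost is one wording change and a few tables, plus some data work. The sponsor must make sure that these values, the local normal ranges and fasting status are entered in the database, since Section 14.2 allows selective entry. Footnotes 3 and 6 of the study calendar must be reconciled on fasting before glucose is graded. Lipids can be graded only at their scheduled visits, so their worst grade may miss changes between them.

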## **12. STATISTICAL METHODS**

### **12.1 Study Design**

This is an open-label, single-arm phase II study of TAK-228 (the ATP-competitive inhibitor of the serine/threonine kinase mTOR) at recommended phase II dosing of 30 mg orally once per week, in subjects with previously treated advanced RCC. The study consists of a two-stage design. The first stage will assess futility when half of the planned patients are enrolled and have had their first (8 week) imaging assessment to determine their response status. The second stage will assess the overall response after all patients are enrolled.

### **12.2 Endpoints**

#### **12.2.1 Definition of Primary Endpoint**

Objective Response (OR): Confirmed CR or PR as best overall response according to RECIST version 1.1 by central review. Objective response will be determined by the best overall confirmed response designation recorded between the date of first dose of trial therapy and the date of objectively documented disease progression or cessation of trial therapy, whichever occurs first. For subjects without documented progression or cessation of trial therapy, all available response designations will contribute to the objective response determination.

#### **12.2.2 Definition of Secondary Endpoints**

- Safety and tolerability according to NCI CTCAE version 4.0
- Progression-free survival (PFS): time from registration to the earlier of (radiographic) progression based on RECIST 1.1 or death due to any cause. Subjects alive without disease progression are censored at date of last disease evaluation.
- Overall survival (OS): time from registration to death due to any cause, or censored at date last known alive.

### **12.3 Sample Size and Accrual**

Forty subjects with metastatic RCC will be enrolled for a goal of 38 evaluable subjects (assuming 5% not evaluable). The two-stage single arm phase II study is designed to detect an improvement in response rate from 5% to 20%. Assuming a type I error of 0.05 and targeting 90% statistical power, 20 patients will be accrued (for 19 evaluable) in the first stage. The first interim analysis will occur when the first 8 week imaging assessment for response data is available for all 20

patients. If 1 or more responses are observed, the accrual will continue to the second stage. Twenty (for 19 evaluable) additional patients will be accrued in the second stage. TAK-228 will be declared ineffective in this study if <5 responses are observed. It will be considered worthy of further study if more than 4 ( $\geq 5$ ) responses are observed.

The design operating characteristics are as follows:

Hypothesis	#s responses at stage I	Prob(stop at first stage)	Overall # responses	Prob(Rx declared inactive)	Design Statistics
Ho: ORR=0.05	<1	38%	$\leq 4$	96%	True type I error 0.04
Ha: ORR=0.2	<1	1.4%	$\leq 4$	10%	Power: 90%

The 90% confidence intervals for the response rate in a two-stage phase II design are summarized as below. The calculation employed the method of Atkinson and Brown (1985) *Biometrics* 741-744

Observed # of responses	Response rate	90% CI
4/38	0.105	(0.04, 0.23)
5/38	0.13	(0.05, 0.26)
6/38	0.16	(0.07, 0.29)
7/38	0.18	(0.09, 0.32)

The accrual is expected to be 3 subjects every month for 14 months to complete enrollment with additional follow-up to 2 years for disease progression or survival. The study is expected to last approximately 40 months.

